1 PROTOCOL SUMMARY

1.1 SYNOPSIS

Title:	Early vs. Interval Postpartum IUD Insertion: A Multi-Site Randomized Controlled Non-Inferiority Trial
Study Description:	This is a randomized controlled non-inferiority trial comparing the expulsion rate of early postpartum IUDs (intrauterine devices) inserted between 2-4 weeks postpartum to the standard interval placement at 6-8 weeks postpartum
Objectives:	Primary Objective: Complete IUD expulsion at 6 months postpartum Secondary Objectives: Partial IUD expulsion at 6 months postpartum, IUD utilization, IUD removal, IUD perforation, pelvic infection, pain, vaginal bleeding, and user satisfaction at 6 months postpartum
Endpoints:	Primary Endpoint: Speculum and ultrasound evaluation Secondary Endpoints: Speculum, ultrasound and x-ray evaluation, self-reported outcomes (survey results)
Study Population:	Postpartum women who delivered an infant within the previous 10 days
Phase:	N/A
Description of Sites/Facilities Enrolling Participants:	Academic medical centers: the University of California, San Diego (UCSD); University of New Mexico (UNM); University of Illinois, Chicago (UIC); and Naval Medical Center, San Diego (NMCS)
Description of Study Intervention:	Postpartum insertion of IUDs at 2-4 weeks after delivery vs. 6-8 weeks after delivery
Study Duration:	2 years
Participant Duration:	6 months (with optional 12-month participation offered)

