2.2 BACKGROUND

Intrauterine devices (IUDs) provide highly effective contraception and are historically placed at the interval six-week postpartum visit for women who desire intrauterine contraception. Since ovulation can occur 25 days postpartum, there is a risk that women could become pregnant between 4-6 weeks postpartum.

Immediate postpartum (IPP) IUD placement, within 10 minutes of delivery, is safe and effective as well as convenient for providers and patients (ACOG, 2016). Despite the benefits of IPP IUD insertion, there are significant barriers to widespread implementation, most importantly a lack of reimbursement mechanisms and training. Although efforts are currently in place to increase access to IPP IUDs, they are developing slowly, and additional strategies are urgently needed to allow for flexibility and multiple options for provision of highly effective contraception in the postpartum period.

Both immediate and interval IUD insertion carry unique risks. IPP IUD insertion is associated with an increased risk of expulsion (IUD being pushed out of the uterus) with rates as high as 24-38% (Chen, 2011; Goldwaite, 2017) compared to IUDs placed at 6 weeks PP 3-5% (Chen, 2011). However, interval IUD insertion at 6 weeks postpartum is associated with a small increase in the risk of uterine perforation (IUD going through the uterine wall), particularly among breastfeeding women (Heinemann, 2015) and there is a risk that women will become pregnant by 6 weeks postpartum leading to undesired pregnancies and rapid repeat pregnancies.

The early postpartum (EPP) period, 2-4 weeks postpartum, could be a convenient time for women to receive contraception, including IUDs. Women can't become pregnant in the first 25 days postpartum. The visit can be co-located with other health care visits, such as well baby visits, that occur in this time frame.

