2. IUD expulsion or uterine perforation risk: there is a risk that IUD expulsion and uterine perforation could be greater than in the study group (EPP) compared to the standard of care group. Currently available data suggest that the risk of expulsion and perforation will be less than or equal to the risk of expulsion and perforation associated with the standard of care. There have been over 200 women who have had documented EPP IUDs placed and the risks of expulsion have been low (<4%) and there have been no documented perforations (Baldwin 2016, Zerden 2017, Chen 2017). In addition, ultrasound studies have shown that approximately two-thirds of uterine involution occurs by 14 days PP which could be protective against expulsion (Belachew, 2012) In the EPP period the uterine wall is thicker than 6 weeks postpartum, which could be protective against perforation (Watanagara, 2015). The practice of inserting IUDs at this time is approved and considered to be a category 2 practice (benefits outweigh the risks) from the CDC Medical Eligibility Criteria (CDC, Medical Eligibility Criteria, 2016). However, the data on this practice are minimal and thus there are potential risks to IUD insertion at this time which is why this study is urgently needed. All patients will be informed of possible IUD expulsion and uterine perforation (known and unknown). Clinicians may also use ultrasound guidance for placement if they feel that ultrasound will mitigate the risk of expulsion or perforation. Participants will be assessed at a follow-up visit for IUD expulsion and uterine perforation. A study clinician will conduct a bimanual pelvic exam and a transvaginal ultrasound at this visit and provide any care clinically required to address any IUD side effects or complications.

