3 OBJECTIVES AND ENDPOINTS

OBJECTIVES	ENDPOINTS	JUSTIFICATION FOR ENDPOINTS
Primary		
To determine if the risk of complete expulsion of EPP IUDs is non-inferior to interval PP IUDs	Diagnosis of IUD expulsion by speculum and ultrasound exam at 6 months postpartum. Expulsion defined as no IUD within the uterus by ultrasound or x-ray.	We propose that greater than or equal to a 6% difference in expulsion at 6 months postpartum between the two arms is clinically meaningful (6% non-inferiority margin).
Secondary		
To assess the proportion of participants utilizing the IUD at 6 months	Transvaginal and speculum exam to confirm presence of the IUD at 6 months.	From a public health perspective, the duration of IUD use is important for pregnancy prevention.
To determine if the risk of partial expulsion of EPP IUDs is non-inferior to interval PP IUDs	Diagnosis of IUD expulsion by speculum and ultrasound exam at 6 months postpartum. Partial expulsion defined as IUD protruding from the external cervical os on speculum exam or any part of the IUD seen below the internal cervical os on transvaginal ultrasound.	We propose that greater than or equal to a 6% difference in partial expulsion and perforation at 6 months postpartum between the two arms is clinically meaningful (6% non-inferiority margin).
Tertiary/Exploratory		
To assess the risk of perforation after EPP IUD compared to interval postpartum IUDs	IUD not visible in uterus on transvaginal ultrasound, but visible on pelvic x-ray at 6 months.	

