All women will be scheduled to have a routine postpartum visit with their designated prenatal care provider **between 42-56 days postpartum** according to the standard of care at the health centers. Women will be scheduled to see a nurse midwife or physician based on their obstetrical history and prenatal care. Women in the interval group will be assessed for IUD placement at this visit per the standard of care at the center. IUDs will be placed by the patient's usual prenatal provider or any provider that the patient would normally be referred to for IUD placement. Whether ultrasound guidance is used for placement will be at the discretion of the clinician. Participants will be compensated with a \$20 gift card for their time and participation. Participants will be asked to complete either the insertion visit questionnaire or the string check questionnaire depending on their assignment group. Providers will be compensated with a \$5 gift card for their time completing a brief questionnaire for every patient seen at six weeks postpartum.

D. Optional String Check Visit:

Whether a follow-up string check visit is scheduled after six weeks will be at the discretion of the clinician according to standard practice of the clinic. String checks are not recommended by the CDC but are common practice. If a string check is scheduled by the clinician at any time (according to their personal practice or participant needs) then the participant will be asked to complete the string check questionnaire at that time.

e. Six Month Follow Up Visit

All women will be scheduled for a 6-month follow up study visit to assess for IUD expulsion, perforation, pregnancy, IUD removals and acceptability. A study clinician will conduct a bimanual pelvic exam, a speculum exam, and a transvaginal ultrasound at this visit. Women will also be asked to complete the 6-month study questionnaire and will be compensated with a \$20 gift card for their time and participation. The clinician will attempt to stay blinded to the participant's group assignment by not reviewing the medical chart prior to the visit.

f. 12 Month Optional Follow Up Call

During baseline survey data collection, all women will be asked if they consent to a 12-month follow up phone call to assess for IUD expulsion, perforation, pregnancy, IUD removals and acceptability.

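### The 6-month visit does not say when the x-ray needed for the perforation endpoint is done, and the complete-expulsion definition also fits a perforated IUD

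*Combined protocol and SAP*

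**What the plan says.** Section 8.1e gives the purpose of the visit: "All women will be scheduled for a 6-month follow up study visit to assess for IUD expulsion, perforation, pregnancy, IUD removals and acceptability". The examinations follow: "A study clinician will conduct a bimanual pelvic exam, a speculum exam, and a transvaginal ultrasound at this visit". Section 2.3.1 has a shorter list for the follow-up visit: "A study clinician will conduct a bimanual pelvic exam and a transvaginal ultrasound at this visit". Neither list mentions an x-ray.

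The endpoint table in Section 3 does rely on one. Perforation, a tertiary/exploratory endpoint, is "IUD not visible in uterus on transvaginal ultrasound, but visible on pelvic x-ray at 6 months". Complete expulsion, the primary endpoint, is to be diagnosed by speculum and ultrasound, with the definition "Expulsion defined as no IUD within the uterus by ultrasound or x-ray". The synopsis (1.1) gives the assessments for secondary endpoints as "Speculum, ultrasound and x-ray evaluation", together with survey results; for the primary endpoint it names only speculum and ultrasound.

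Three later sections use these outcomes. The footnote to Section 9.3 accepts an outcome as known from ultrasonography, pelvic examination or a contact, and does not mention x-ray. Section 9.4.3 analyses perforation by the methods used for the primary outcome. Section 8.2 counts perforation among the serious events whose rate can convene the DSMB.

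**The concern.** There are two gaps.

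The first is ascertainment. The examinations listed for the visit cannot on their own satisfy the perforation definition, because half of that definition is an x-ray finding. If each of the four sites decides for itself when to obtain an x-ray, ascertainment may differ between sites. It may also differ between arms, since the protocol says only that the examining clinician will attempt to stay blinded.

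The second is definition. Perforation and complete expulsion are not mutually exclusive as written, so perforations can enter the primary endpoint. Few expulsions are expected, so one or two such women per arm would be noticeable. Depending on the arm in which they fall, they could make non-inferiority easier or harder to show. The perforation comparison and the DSMB trigger rest on the same unresolved classification.

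**Working it through.** **1. The definitions applied to each true state of the device**

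| True state | Ultrasound | X-ray | Complete expulsion (Sec. 3)? | Perforation (Sec. 3)? |
|---|---|---|---|---|
| Out of the body | uterus empty | none seen | met | not met |
| Outside the uterus, x-ray done | uterus empty | device seen | met (read literally) | met |
| Outside the uterus, no x-ray | uterus empty | not available | met (read literally) | cannot be established |

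The third row comes from the missing x-ray trigger. The second comes from the expulsion definition and would remain if an x-ray were added to the visit. No section gives a precedence rule for either row.

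**2. The plan's own sample size (Section 9.2), for context**

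Inputs: 4% in both arms, margin 6 points, two-sided alpha 0.05, power 80%.

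n = (1.960 + 0.8416)² × 2 × 0.04 × 0.96 / 0.06² = 7.849 × 0.0768 / 0.0036 = 167.4, so 168 evaluable per arm. 168 × 1.20 = 201.6, so 202 per arm and 404 in total. The plan's figure is reproduced.

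Applying the stated losses to 202 gives 202 × 0.85 × 0.95 = 163 evaluable per arm, which is used below.

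**3. How much room there is**

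Expected complete expulsions at 4%: 0.04 × 163 = 6.5 per arm. One reclassified woman moves an arm's rate by 1/163 = 0.61 points.

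**4. Effect on the non-inferiority decision**

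The documents give no perforation rate. I assume that 0.1% to 1% of women have a perforation counted as an expulsion, which is 0.16 to 1.63 women per arm. For event counts x (early) and y (interval), non-inferiority is declared when

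(x − y)/n + 1.96 × √[p₁(1 − p₁)/n + p₂(1 − p₂)/n] < 0.06, with p₁ = x/n, p₂ = y/n, n = 163.

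Exact binomial probabilities are summed over all (x, y) that meet this condition. False non-inferiority starts from true expulsion of 10% early v 4% interval (the margin); power starts from 4% in both arms. The assumed rate is added to the arm or arms shown.

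| Perforations counted as expulsions | False non-inferiority | Power |
|---|---|---|
| None | 3.3% | 78.9% |
| Interval arm only, 0.1% | 3.5% | 79.8% |
| Interval arm only, 1% | 6.4% | 86.5% |
| Both arms, 0.1% | 3.3% | 78.1% |
| Both arms, 1% | 3.1% | 71.0% |
| Early arm only, 1% | 1.5% | 59.9% |

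The 3.3% with no misclassification is already above 2.5%. That comes from the Wald interval and is separate from this point. With 168 per arm the corresponding values are close: 3.2% with none, and 6.4% with 1% in the interval arm only.

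**The case against.** The strongest reply is that the examination list in 8.1e need not be exhaustive. An x-ray makes sense only after an ultrasound that shows no device, so a list written for all women would naturally leave it out. Section 3 places the x-ray at 6 months, the synopsis names it, and Section 2.3.1 has the clinician provide clinically required care at follow-up. The list in 2.3.1 also omits the speculum exam that 8.1e includes, so these lists are plainly abbreviated. This stands. A reader might infer that no perforation can be recorded at the visit, or that the comparison must be zero against zero. The documents do not support that: nothing excludes the x-ray, and perforations can also surface as serious events (8.2) or through adverse event reporting (8.3.4).

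A reader might also infer that a device not seen on ultrasound is scored as an expulsion by rule. No such scoring rule is written; it is a literal reading of the Section 3 definition.

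Nor do the documents establish that the error favours non-inferiority. Section 2.2 says that "interval IUD insertion at 6 weeks postpartum is associated with a small increase in the risk of uterine perforation", but gives no figure. Section 2.3.1 says the thicker early uterine wall could be protective, yet also allows that perforation could be more frequent in the early group and calls the data minimal.

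The reply does not answer two things: the trigger for the x-ray is nowhere stated, and the two definitions overlap even when the x-ray is done.

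**Conclusion.** The point holds as an unspecified assessment and an overlapping primary-endpoint definition. It is not proof that perforation goes unmeasured or that the result is biased in a known direction. The overlap matters more, because it lies in the definition of the primary outcome and adding an x-ray would not remove it.

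The size is conditional on assumed rates of 0.1% to 1%, with every such perforation counted as an expulsion. If they fall only in the interval arm, false non-inferiority rises from 3.3% to between 3.5% and 6.4%. If rates are equal, it stays at 3.1% to 3.3% and the cost is power, about 8 points at 1%. If 1% falls only in the early arm, power drops by about 19 points. At the low end of the range the effect is negligible. The correction is still worth making, because the outcome is rare and the change is one of wording.

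**What to change.** Reconcile Sections 2.3.1, 3 and 8.1e with the synopsis.

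- **Section 3:** amend the definition of complete expulsion so that it and perforation are mutually exclusive. A device located outside the uterus on x-ray is a perforation and not an expulsion.
- **Section 8.1e:** state that the pelvic x-ray already named in Section 3 is the study assessment for a device not seen on ultrasound and not documented as expelled or removed. This concerns how the endpoint is established; clinical management is outside this point.
- **Scoring:** a woman with no device on ultrasound, no x-ray and no documented expulsion or removal is classed as location unresolved, not as a confirmed expulsion.
- **Section 9.4.2:** add a sensitivity analysis that counts unresolved women first as expulsions and then as non-expulsions, and report their number by arm.

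The cost is a few lines of text, one extra sensitivity analysis and a small number of x-rays that the endpoint table already implies. At the assumed 4%, about 0.04 × 326 = 13 women in total would have an expelled device, and those with a documented expulsion would not need the x-ray for this purpose.

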4 STUDY DESIGN

4.1 OVERALL DESIGN

This is a multi-site, two-arm, non-blinded randomized controlled non-inferiority trial that includes 6 months of participation from enrollment to final follow-up.

Hypothesis: We hypothesize that the EPP IUD expulsion rate at 6 months postpartum will be lower than the reported expulsion rate for IPP IUDs (24%) and non-inferior at a 6% margin to the expulsion rate for interval postpartum IUDs (previously reported at 3-5%).

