6.2 MEASURES TO MINIMIZE BIAS: RANDOMIZATION AND BLINDING

Participants will be randomized to receiving EPP or Interval IUD placement by chance with a computer-generated randomization scheme in alternating blocks of 4 and 6 stratified by IUD type and site. The group assignment will be in opaque sealed envelope that will be opened by the research assistant. The participant will not be blinded to the group assignment.

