For women who believe they want an IUD postpartum but are unsure whether or not they would like to be part of the study, study staff will provide them with our contact information, an informed consent form, a Subject's Bill of Rights, and a HIPAA Authorization form for medical data to be released for research purposes. If they decide they are interested in participating while they are still in the hospital, the RA will go to their postpartum floor within 24 hours and will pre-screen/enroll as outlined above. For interested women who are being discharged from the hospital, staff will ask them to call us to discuss the study. Over the phone, the RA will ask for verbal consent to pre-screen for the study. If a woman gives verbal consent to be pre-screened, the RA will administer the Pre-Participation Questionnaire/Eligibility Checklist. For women who meet inclusion criteria, meet no exclusionary criteria, and want to participate, the RA will review the Informed Consent and HIPAA Authorization forms and then ask the woman to sign the forms and bring the signed copies to their first study visit. The woman will be officially enrolled in the study at that point. The RA will then open the randomization envelope and schedule the first study visit at either 2 weeks or 6 weeks postpartum once the consent is

signed. The RA will administer the Enrollment Survey either over the phone or in person before the first research visit.

b. Two Week Postpartum Visit

All women randomized to EPP will be scheduled to have an IUD placement visit with their designated prenatal care provider **between 14 and 28 days**. Women will be scheduled to see a nurse midwife or physician based on their obstetrical history and prenatal care. IUDs will be placed by the patient's usual prenatal provider or any provider that the patient would normally be referred to for IUD placement. Whether ultrasound guidance is used for placement will be at the discretion of the clinician. Participants will be compensated with a \$20 gift card for their time and participation after completing the IUD Insertion survey. If a patient in the interval group is seen by her provider at 2 weeks postpartum for other reasons an IUD will not be placed at that visit. Providers will be compensated with a \$5 gift card for their time completing a brief questionnaire for every patient seen at 2 weeks who is participating in the study.

c. Six Week Postpartum Visit

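### The 6-month examiner's blinding rests only on not reading the chart, which leaves the secondary partial-expulsion reading open to avoidable assessment bias

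*Combined protocol and SAP*

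**What the plan says.** Section 4.1 describes a "multi-site, two-arm, non-blinded randomized controlled non-inferiority trial", and section 6.2 adds: "The participant will not be blinded to the group assignment".

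Sections 8.1b and 8.1c leave insertion to routine care: "IUDs will be placed by the patient's usual prenatal provider or any provider that the patient would normally be referred to" for that purpose. Section 8.1e then states: "A study clinician will conduct a bimanual pelvic exam, a speculum exam, and a transvaginal ultrasound at this visit". The women also complete the 6-month questionnaire at that visit, and the visit covers perforation, pregnancy, removals and acceptability as well as expulsion. The examiner is to try to remain blinded, and the one method named is "by not reviewing the medical chart prior to the visit".

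The objectives table in section 3 defines the two expulsion endpoints:
- Complete expulsion (primary): "Expulsion defined as no IUD within the uterus by ultrasound or x-ray".
- Partial expulsion (secondary): the device protrudes from the external os on speculum, or there is "any part of the IUD seen below the internal cervical os on transvaginal ultrasound".

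Section 9.1 gives partial expulsion its own non-inferiority hypothesis at 6%, and section 9.4.3 analyses it as the primary outcome is analysed. Section 9.1 also lists satisfaction with the timing of placement as an outcome.

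**The concern.** By asking the examiner to stay blinded, the plan accepts that knowledge of the arm could influence the reading. Leaving the chart closed shuts one route and leaves three open.

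- **The woman.** She knows when her IUD was placed, and nothing asks her not to say so.
- **The visit.** No order is set between the examination and the questionnaire or history. Timing of placement is itself a subject of the trial's self-reported outcomes.
- **The examiner.** No text separates the person who inserted a woman's device from the person who examines her. An inserter might remember the timing without a chart.

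The plan also has no record of whether the examiner became aware of the arm, so the trial could not report how well the blind held. At stake is a formal non-inferiority conclusion on partial expulsion. A lenient reading of borderline early-arm scans would favour non-inferiority, and a strict one would work against it.

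**Working it through.** **1. Which endpoint is exposed.** Complete expulsion depends on whether a device is in the uterus on imaging, which leaves little room for interpretation. The speculum criterion for partial expulsion is direct observation. The ultrasound criterion follows a written anatomical rule, but the operator must still locate the device relative to the internal os on a live scan, and no second reading is planned. The exposure is therefore mainly to this one criterion of a secondary endpoint.

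**2. Inputs for an illustration.**
- Randomised per arm: 202 (section 9.2).
- Losses: 15% to follow-up and 5% not placed (section 9.2). Evaluable: 202 × (1 − 0.15 − 0.05) = 161.6, taken as 162.
- Margin: 6 percentage points (section 9.1). Method: Wald, with the interval compared with the margin (sections 9.4.2 and 9.4.3).
- Interval level: taken as 95% two-sided. Section 9.2 gives both two-sided 0.05 and one-sided 0.25%. Only one-sided 2.5% reproduces the planned size: 2 × 0.04 × 0.96 × (1.960 + 0.842)² / 0.06² = 167.4, so 168; 168 × 1.20 = 201.6, so 202 per arm and 404 in total.
- Partial-expulsion rate: 2–5% at 6 months (section 2.2). This comes from studies of early placement. The documents give no interval-arm rate, so using it there is an assumption: 162 × 0.02 = 3.2 and 162 × 0.05 = 8.1, hence 3 to 8 events.

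**3. Formula.** With e early and c interval events and n = 162 per arm, p₁ = e/n and p₀ = c/n. Upper limit = (p₁ − p₀) + 1.96 × √[p₁(1 − p₁)/n + p₀(1 − p₀)/n]. Non-inferiority needs an upper limit below 6%.

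Example with c = 6:
- e = 8: difference 1.235%, SE 2.258%, upper limit 1.235 + 1.96 × 2.258 = 5.66%, which passes.
- e = 9: difference 1.852%, SE 2.332%, upper limit 1.852 + 1.96 × 2.332 = 6.42%, which fails.

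**4. Results across the assumed range.**

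| Interval events | Largest early count that passes (upper limit) | First that fails (upper limit) | Extra early events needed to fail |
|---|---|---|---|
| 3 | 6 (5.42%) | 7 (6.23%) | 4 |
| 4 | 7 (5.79%) | 8 (6.57%) | 4 |
| 5 | 7 (5.35%) | 8 (6.12%) | 3 |
| 6 | 8 (5.66%) | 9 (6.42%) | 3 |
| 7 | 9 (5.95%) | 10 (6.70%) | 3 |
| 8 | 9 (5.47%) | 10 (6.22%) | 2 |

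From equal counts, 2 to 4 additional early-arm events lose non-inferiority.

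**5. What this does not give.** The documents contain no misreading rate and no indication of which way an unblinded examiner would lean. The table shows how few readings separate the two conclusions. It does not estimate bias.

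**The case against.** The strongest reply is that the trial is openly non-blinded, that the attempt at examiner blinding is a pragmatic extra, and that both forms of expulsion have written definitions. Much of this stands.

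- A reader might infer that the primary result is compromised. The documents do not support that, because absence of the device on imaging is hard to misread.
- A reader might infer that inserters will examine their own patients. The plan uses different labels for the two roles and says nothing of overlap, so the point rests on silence. An examiner asked to stay blinded would also sit awkwardly with having inserted that woman's device.
- A reader might infer that the questionnaire itself unblinds the examiner. Section 8.1e says that women complete it, not that the examiner administers it, and elsewhere a research assistant handles the surveys.
- A reader might take 6 against 8 or 9 events to mean that a single borderline reading typically decides the trial. That starts one event from the boundary. Any threshold test has adjacent counts that pass and fail, even under perfect blinding.

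What remains is that the plan sets itself a blinding aim and gives it a weak means, although better ones cost little. Changes to 8.1e will not reach every event: section 9.3 also accepts outcomes from ultrasonography, pelvic examination or a contact up to 240 days.

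**Conclusion.** The concern holds in limited form, as a cheap improvement of minor severity. Chart avoidance is the only blinding step, and it leaves disclosure by the woman, visit order and examiner identity uncontrolled. The consequence falls mainly on the ultrasound component of partial expulsion, with little effect on the primary endpoint. Size and direction of bias cannot be derived. The figure of 2 to 4 extra early-arm events is an illustration, conditional on 162 evaluable per arm, a 95% Wald interval and the early-placement rate of 2–5% carried over to the interval arm.

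**What to change.** In section 8.1e, state that:

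1. the speculum and ultrasound examination is done and recorded before the questionnaire or any history of insertion;
2. the woman is asked beforehand not to mention when her IUD was placed;
3. where site staffing allows, the examiner is an existing study clinician who did not insert that woman's IUD, and otherwise the examination is recorded as unblinded;
4. the examiner records whether the allocation became known, and the frequency is reported by arm.

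Report unblinding descriptively only. A sensitivity analysis restricted to examinations where the blind held should not be added. It conditions on an event after randomisation, women with symptoms or device problems may be likelier to disclose, and the restricted comparison would lose both randomisation and precision.

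The cost is protocol wording, one line of script and one form field. The documents give no site staffing, so item 3 is conditional; expect minor scheduling limits at small sites. Sample size is unchanged.
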